- If the current dose level  $j$  is the lowest dose, treat the new patients at the lowest dose unless the RDS of the lowest dose is “E,” at which point terminate the trial.
- If the current dose level  $j$  is not the lowest dose and the RDS of dose level  $j - 1$  is not “E,” de-escalate the dose to level  $j - 1$  to treat the next cohort of patients.
- If the current dose level  $j$  is not the lowest dose and the RDS of dose level  $j - 1$  is “E,” stay at the current dose level  $j$  to treat the next cohort of patients unless the RDS of dose level  $j$  is “E,” at which point terminate the trial.

3. Repeat step 2 until the maximum sample size of 21 is reached or if the number of patients treated on any dose reaches 12. Then, use the isotonic estimation method described in Lin et al. (Lin et al., 2020) to select the (biologically optimal) dose that is admissible and that has the highest estimated utility.

**We have treated 6 patients on the study so far. The first 3 patients were treated at the dose level of 5 mg and the next 2 patients at dose level 7.5 mg. The three patients treated at 7.5 mg CMP001 dose will be included to the maximum accrual goal of 21 with this updated protocol. (Previous version had target accrual of 39 patients). This means additional 18 patients are needed to complete the study. Patients treated at 5 mg included 2 patients with recent anti-B cell therapy (Rituximab, CAR T cells) and did not develop antiQbeta antibody important for CMP001 function. We updated the exclusion criteria to account for this observation.**

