### 2.1.3 Dose-Limiting Toxicities

The DLT observation period is 15 days from date of first (W1D1) CMP-001 injection (i.e., following 3 doses of CMP-001; W1D1, W2D1, W3D1). Subjects who have received at least one dose of CMP-001 and pembrolizumab are evaluable for DLT assessments.

DLTs are defined below and only include AEs that are considered possibly, probably, or definitely related to the CMP-001 plus pembrolizumab combination. Attribution of AEs specifically to either CMP-001 or pembrolizumab is challenging, therefore, the relationship to CMP-001 should be based on attribution to the combination of the two study drugs (CMP-001 + pembrolizumab).

The following AEs will be considered DLTs **if deemed related to study drug combination**:

- Hematologic
  - Grade 4 neutropenia
  - Febrile neutropenia, defined as absolute neutrophil count (ANC) <1000/mm^3 with a temperature of  $\geq 38.3$  degrees C
  - Grade  $\geq 3$  neutropenic infection
  - Grade  $\geq 3$  thrombocytopenia with clinically significant bleeding seeking medical intervention
  - Grade 4 thrombocytopenia
- Non-hematologic:
  - Grade  $\geq 3$  toxicities (non-laboratory); excluding:
    - Grade 3 fatigue lasting <7 days
    - Grade 3 arthralgia or myalgia that downgrades to less or equal to grade 2 within 3 days of supportive care
    - Grade 3 pain at injection site that downgrades to less than or equal to Grade 2 within 3 days of supportive care

- Grade 3 electrolyte abnormalities that are asymptomatic and reversed with medical intervention within 3 days
  - Grade  $\geq 3$  nausea, vomiting or diarrhea despite maximal medical intervention
  - Grade 4 aspartate aminotransferase (AST) and alanine aminotransferase (ALT) unless alternate explanations such as viral hepatitis or disease progression in the liver
- Other (non- AST/ALT) non-hematologic Grade  $\geq 3$  laboratory value if the abnormality leads to overnight hospitalization

[figure not shown]
[figure not shown]

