8. Patients previously treated with anti B cell directed therapy, such as anti-B cell antibody therapy within the past year or a history of CAR T therapy at any time, will be evaluated for the presence of B cells by flow cytometry on peripheral blood. Patients with  $> 100$  benign B cells will be considered eligible. Those with  $\leq 100$  benign B cells may still be enrolled at the investigator's discretion but will only proceed to the therapeutic phase of the study if they have been shown to generate an anti-Qbeta antibody response, as demonstrated by ELISA assay, in response to the priming dose of vidutolimod. (Trial Schema, section 2.2)

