## 7.0 TRIAL FLOW CHART

Procedure or Assessment	Screening (Day -21 to -1) a	W1 D1	W2 D1	W3 D1	W4 D1	W5 D1	W6 D1	W7 D1	W10 D1	Every 3 Weeks Post W10 (W13, W16 etc.)	End of Treatment b	30 Day Follow up visit n	Long Term Survival Follow-up o
CMP-001 Dose Number	n/a	1	2	3	4	5	6	7	8	9+	n/a	n/a	n/a
Visit Windows	n/a	n/a	±2 days	±2 days	±2 days	±2 days	±2 days	±2 days	±7 days	±7 days	±7 days	±7 days	± 1 month
Informed Consent	X												
Eligibility Criteria Assessment	X												
Medical History, Demographics, Cancer History including Prior Cancer Medications	X												
Physical Exam c	X	X		X	X			X	X	X	X		
Vital Signs d	X	X	X	X	X	X	X	X	X	X	X		
ECOG Performance Status	X	X		X	X			X	X	X	X		
Body Weight	X	X			X			X	X	X	X		
Height	X												
Electrocardiogram (ECG) e	X	X		X				X			X		
Autoimmune lab panel f	X										X		
Clinical Laboratory Tests (hematology, serum chemistry, urinalysis) g	X	X	X	X	X	X	X	X	X	X	X		
Coagulation Tests (PTT & INR) h		X						X	X	X			
Thyroid Function Tests	X			X				X			X		
Research blood Samples i	X	X		X			X		X	-			
Tumor Biopsy j	X			X			X		X	-			
Urine Pregnancy Test k	X	X			X			X	X	X	X		
Disease Assessment (PET-CT/CT) a, l	X	At W7D1 (or two cycles) and then as clinically indicated											
Adverse Event Monitoring n		Assessed continually from W1D1 through EOT +30 days											
Concomitant Medications		Assessed continually from 28 days prior to first CMP-001 dose through EOT +30 days											
CMP-001 dosing m		X	X	X	X	X	X	X	X	X			
Pembrolizumab Dosing		Pembrolizumab will be given according to pembrolizumab label (every 3 week)											

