- i. Blood samples (20 ml) for research including exploratory biomarker, immunogenicity studies, and assessment of pharmacodynamics are to be collected at screening and then on following days and times:  
 Blood draw pre-treatment W1D1 or before, W3D1, W6D1, W10D1 prior to dosing with CMP-001 – Additional blood draw with subsequent cycles may be requested.
- j. Archival tumor samples should be identified at Screening, if available for potential access later. Additional tumor biopsies are optional and may be collected at other times then specified below at the discretion of the Investigator. Optional tumor biopsies (fresh frozen when feasible and typically FNA), will be collected prior to starting treatment on W1D1, W3D1, W6D1, W10D1. If pre-treatment biopsy prior to W1D1 treatment not done, it can be scheduled with W2D1 intra-tumor injection.
- k. In women of childbearing age, Urine pregnancy testing should be performed at Screening and prior to 1st CMP-001 injection (W1D1), prior to 4th CMP-001 injection (W4D1), prior to 7th CMP-001 injection (W7D1), followed by every 3 weeks prior to treatment and EOT. A negative test within 72 hours of treatment is acceptable.
- l. CT neck/chest/abdomen/pelvis with contrast or PET-CT scans to assess response will be at W7D1 (or after two cycles) and then as clinically indicated. Subjects may be asked to provide historical scans (scans performed prior to Screening) for informational purposes prior to starting CMP-001 therapy, if available.
- m. The first CMP-001 injection stimulates antibody formation to the VLP of CMP-001 and will be given subcutaneously. Subsequently, CMP-001 should be administered as close to the tumor as possible if intratumoral injection not possible. A window of  $\pm 2$  day is permitted for the CMP-001 dose schedule for the first weekly CMP-001 injections and a window of  $\pm 7$  days is permitted for every 3 week CMP-001 injections. To assure maximum effectiveness, consecutive IT injections of CMP-001 should always be administered at least 96 hours apart. No CMP-001 dose should be skipped. If a CMP-001 dose needs to be delayed due to toxicity the dose should be completed as soon as the toxicity has resolved.

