## **8.0 TRIAL PROCEDURES**

### **8.1 Trial Procedures**

The Trial Flow Chart - Section 7.0 summarizes the trial procedures to be performed at each visit. Individual trial procedures are described in detail below. It may be necessary to perform these procedures at unscheduled time points if deemed clinically necessary by the investigator.

Furthermore, additional evaluations/testing may be deemed necessary by the Sponsor and/or Merck for reasons related to participant safety. In some cases, such evaluation/testing may be potentially sensitive in nature (e.g., HIV, Hepatitis C, etc.), and thus local regulations may require that additional informed consent be obtained from the participant. In these cases, such evaluations/testing will be performed in accordance with those regulations.

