#### **8.1.4.2 Immunogenicity**

Plasma will be assayed for the presence of anti-pembrolizumab and anti-Qbeta capsid protein antibodies as per Trial Flow Chart, 7.0.

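### No anti-Qbeta sample is scheduled before the W2D1 dose that depends on it, the 15-day DLT window does not allow for the resulting hold, and the only safety population omits treated patients without a response assessment

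*Combined protocol and SAP*

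**What the plan says.** - **Antibody condition (5.1, no. 8).** It applies after anti-B cell antibody therapy within the past year, or CAR T therapy at any time, when the benign B cell count is 100 or lower. The investigator may enrol such patients, but they "will only proceed to the therapeutic phase of the study if they have been shown to generate an anti-Qbeta antibody response". The response is to the priming dose, is measured by ELISA, and the criterion points to the section 2.2 schema.
- **Assay timing (8.1.4.2).** "Plasma will be assayed for the presence of anti-pembrolizumab and anti-Qbeta capsid protein antibodies as per Trial Flow Chart, 7.0".
- **Draw days (7.0, footnote i).** After screening: "Blood draw pre-treatment W1D1 or before, W3D1, W6D1, W10D1 prior to dosing with CMP-001". The research blood row is blank at W2D1, although the row "Clinical Laboratory Tests (hematology, serum chemistry, urinalysis") is marked there.
- **Delays (footnote m; 8.1).** Doses are not to be skipped, and the only delay described is for toxicity: "If a CMP-001 dose needs to be delayed due to toxicity the dose should be completed as soon as the toxicity has resolved". Section 8.1 adds: "It may be necessary to perform these procedures at unscheduled time points if deemed clinically necessary by the investigator".
- **DLT window (2.1.3).** "The DLT observation period is 15 days from date of first (W1D1) CMP-001 injection", explained as following the W1D1, W2D1 and W3D1 doses. One dose each of CMP-001 and pembrolizumab makes a patient DLT-evaluable.
- **Replacement (5.5).** Non-DLT withdrawals before the end of a 21-day period are replaced.
- **Analysis sets (9.3).** Safety and efficacy share one population: at least one CMP-001 dose and at least one recorded response assessment after baseline. Section 9.5 refers to a Safety Population that is not defined separately.

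**The concern.** The antibody condition answers a problem seen in this trial. Section 2.1.2 says of the 5 mg group that it "included 2 patients with recent anti-B cell therapy (Rituximab, CAR T cells) and did not develop antiQbeta antibody important for CMP001 function". The protocol regards the antibody as important for the drug to work, yet the schedule that times the assay gives no result before the first intratumoral dose.

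A hold on dose 2 then meets a DLT window tied to W1D1 rather than to exposure. Section 4.1.1.1 says cytokine-release events typically present after the third CMP-001 dose. A held patient could pass through the window with only one or two doses and be recorded as free of DLT.

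The population definition is a wider matter. A safety population conditional on having a response assessment selects on staying in the trial. Patients who stop early for toxicity are the ones most likely to be missing from it.

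**Working it through.** **Inputs.** Days are counted as elapsed from W1D1 (day 0). From 7.0 and footnote m: dose 2 on day 7, dose 3 on day 14, each ±2 days; consecutive doses at least 96 hours (4 days) apart; first response scan at W7D1, day 42. From 2.1.3: window end on day 15. From 5.5: replacement limit of 21 days. ELISA turnaround *t* is not given; 0 to 10 days is assumed.

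**1. The plan's own figure.** With no hold, doses fall on days 0, 7 and 14. All three lie within 15 days, so the stated window reproduces. The margin after an on-time third dose is 15 − 14 = 1 day. If 15 days means study day 15 (14 elapsed), the margin is zero.

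**2. Samples before dose 2.** Dose 2 falls between days 5 and 9. Scheduled post-priming draws are on days 14, 35 and 63. None precedes dose 2. On schedule, the day-14 draw follows one intratumoral dose and so does not show the response to priming alone.

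**3. Effect of a hold.** If dose 2 is held *h* days, dose 3 falls on day 14 + *h* at weekly spacing, or 7 + *h* + 4 = 11 + *h* at the 96-hour minimum. It lies within day 15 only if *h* ≤ 1 or *h* ≤ 4 respectively. Each limit is one day lower if the window ends at 14 elapsed.

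| Sample used | Dose 2 given | Dose 3, weekly | Dose 3, 96 h | Dose 3 within day 15? |
|---|---|---|---|---|
| Pre-dose W2D1 (day 7, not scheduled) | 7 + *t* | 14 + *t* | 11 + *t* | *t* ≤ 1 weekly; *t* ≤ 4 at 96 h |
| W3D1 (day 14, scheduled) | 14 + *t* | 21 + *t* | 18 + *t* | never |

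Taking the W3D1 draw at the early end of its visit window (day 12) gives dose 3 no sooner than 12 + 4 = 16, still outside.

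**4. Replacement limit.** A W2D1 result arrives on day 7 + *t*, at most day 17, within the 21 days. A W3D1 result arrives on day 14 + *t*, which falls within 21 days only if *t* is no more than about 6.

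**5. Safety population.** This needs no model. Membership requires a response assessment, the first is scheduled for day 42, and the flow chart marks no scan at End of Treatment. A treated patient who leaves before day 42 and is not scanned for clinical reasons is outside the only population labelled for safety. As an illustration, take a dose group at the 12-patient cap of 2.1.2 with *k* patients having a given severe event, one of whom leaves unscanned. The reported rate changes from *k*/12 to (*k* − 1)/11:

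- *k* = 1: 8.3% to 0%
- *k* = 2: 16.7% to 9.1%
- *k* = 3: 25.0% to 18.2%
- *k* = 4: 33.3% to 27.3%

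That is 6 to 8 percentage points for one omitted patient. The documents give no rate of early departure.

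**The case against.** The strongest reply is that the antibody condition itself implies a hold. Once dose 2 is held, the W3D1 draw is taken before dosing, follows priming alone, and can answer the question, though late. Section 8.1 also permits unscheduled procedures, and the section 2.2 schema may show both the test and the hold. All of this stands. A reader might infer that the condition cannot be run, or that the site is left to improvise; the documents do not support that.

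The safety loss in a held patient is also limited. Section 4.1.1.1 describes the cytokine-release events as predominantly Grade 1–2 and resolving within hours. Section 2.1.3 excludes from DLT such events of Grade 3 or below that settle to Grade 1 or below within 24 hours. Only more severe or prolonged events are at stake, and AEs are collected to 30 days after end of treatment in any case.

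Two further inferences are tempting:

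- **A rate of affected patients from those treated so far.** Section 2.1.2 reports antibody status only for 5 mg patients, not for those at 7.5 mg. The two cases led to the eligibility change; they are not failures of it.
- **Distorted dose elimination if a patient who fails the antibody test is counted in Table A.** Section 2.1.2 and Appendix F count evaluable patients, which points towards leaving such a patient out, though neither names the case. Nothing here shows that a too-toxic dose becomes harder to eliminate.

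On section 9.3, a detailed SAP is promised in 9.1 and could separate the two populations. Until it does, the stated rule is the combined one.

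**Conclusion.** The point holds in two parts of different weight.

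**Antibody test and DLT window: minor.** The schedule that 8.1.4.2 relies on has no sample between priming and dose 2. Using scheduled samples alone, dose 2 must wait about a week or more, and dose 3 then always falls outside the DLT window. With a W2D1 sample, dose 3 stays inside only if the turnaround is at most 1 day at weekly spacing, or 4 days at the 96-hour minimum. This rests on an assumed turnaround and on the visible text. The schema may already supply the test and the hold, in which case the flow chart and 2.1.3 still need to match it. Enrolling these patients is discretionary, so the number affected may be zero.

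**Safety population: moderate.** This applies to every patient and does not depend on the schema or the turnaround. The definition in 9.3 removes treated patients without a response assessment from the safety summaries, and early toxicity is one route to that. A reader might infer that their safety data are lost. They are not: the events are still collected and reported, and DLT evaluability in 2.1.3 requires no scan. The fault lies in which patients the summaries describe.

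**What to change.** 1. **Section 9.3.** Define the safety population as all patients who received at least one dose of CMP-001, separate from the response-evaluable population. This costs only wording.
2. **Flow chart and footnotes i and m.** For patients with 100 or fewer benign B cells, add a pre-dose W2D1 anti-Qbeta sample and hold dose 2 until the result. Make this agree with the section 2.2 schema. Section 4.3.1 expects an adequate antibody response within a week of the first dose, so W2D1 is a reasonable time. The cost is one tube at a visit that already draws blood, plus the ELISA wait.
3. **Sections 2.1.3 and 5.5.** For held patients, end the DLT window at the later of day 15 or 1 day after the third CMP-001 dose, and extend the 21-day replacement limit to the end of that window. In the assumed range the latest end is 7 + 10 + 7 + 1 = day 25. Without the second change, a held patient withdrawing after day 21 but before day 25 would neither complete the window nor be replaced. Cohort decisions should not slow down, because 2.1.2 already waits for efficacy evaluability and the first scan is on day 42.
4. **Clarification only.** State that patients who fail the antibody test, receive no intratumoral CMP-001 and have no DLT are not counted in Table A and are replaced. The cost is an occasional replacement.

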## 5.2 Participant Exclusion Criteria

Participants are excluded from the study if any of the following criteria apply:

1. A WOCBP who has a positive urine pregnancy test within 72 hours prior to first dose of study drug. (see Appendix C). If the urine test is positive or cannot be confirmed as negative, a serum pregnancy test will be required.
2. Has received prior therapy with an anti-PD-1, anti-PD-L1, or anti-PD-L2 agent or with an agent directed to another stimulatory or co-inhibitory T-cell receptor (eg, CTLA-4, OX-40, CD137) within 4 weeks of enrollment into this trial.
3. Has received prior systemic anti-cancer therapy including investigational agents within 4 weeks or within 5 half-lives, whichever is shorter, prior to first dose of study drug.

Note: Participants must have recovered from all AEs due to previous therapies to  $\leq$  Grade 1 or baseline. Participants with  $\leq$  Grade 2 neuropathy may be eligible.

Note: If participant received major surgery, they must have recovered adequately from the toxicity and/or complications from the intervention prior to starting study treatment.

4. Has received prior radiotherapy within 2 weeks of start of study treatment. Participants must have recovered from all radiation-related toxicities, not require corticosteroids, and not have had radiation pneumonitis. A 1-week washout is permitted for palliative radiation ( $\leq 2$  weeks of radiotherapy) to non-CNS disease.
5. Has received a live vaccine or live-attenuated vaccine within 30 days prior to the first dose of study drug. Administration of killed vaccines is allowed.
6. Is currently participating in or has participated in a study of an investigational agent or has used an investigational device within 4 weeks, or within 5 half-lives, whichever is shorter, prior to the first dose of study treatment.  
Note: Participants who have entered the follow-up phase of an investigational study may participate as long as it has been 4 weeks, or 5 half-lives, whichever is shorter, after the last dose of the previous investigational agent.
7. Has a diagnosis of primary immunodeficiency disorder or is receiving chronic systemic steroid therapy (in dosing exceeding 10 mg daily of prednisone equivalent) or any other form of immunosuppressive therapy within 7 days prior to the first dose of study drug.
8. Has a known additional malignancy that is progressing or has required active treatment within the past 3 years. Note: Participants with basal cell carcinoma of the skin, squamous cell carcinoma of the skin, or carcinoma in situ (e.g. breast carcinoma, cervical cancer in situ) that have undergone potentially curative therapy are not excluded.
9. Has known active CNS metastases and/or carcinomatous meningitis. Participants with previously treated brain metastases may participate provided they are radiologically stable, i.e. without evidence of progression for at least 4 weeks by repeat imaging (note that the repeat imaging should be performed during study screening), clinically stable and without requirement of steroid treatment for at least 14 days prior to first dose of study treatment.
10. Has severe hypersensitivity ( $\geq$ Grade 3) to pembrolizumab and/or any of its excipients.
11. Has active autoimmune disease that has required systemic treatment in the past 2 years (i.e. with use of disease modifying agents, corticosteroids or immunosuppressive drugs). Replacement therapy (eg., thyroxine, insulin, or physiologic corticosteroid replacement therapy for adrenal or pituitary insufficiency, etc.) is not considered a form of systemic treatment.
12. Has a history of (non-infectious) pneumonitis/interstitial lung disease that required steroids or has current pneumonitis/interstitial lung disease.
13. Has an active infection requiring systemic therapy.
14. Has a known history of Human Immunodeficiency Virus (HIV). Note: No HIV testing is required unless mandated by local health authority.

15. Has a known history of Hepatitis B (defined as Hepatitis B surface antigen [HBsAg] reactive) or known active Hepatitis C virus (defined as HCV RNA is detected) infection. Note: no testing for Hepatitis B and Hepatitis C is required unless mandated by local health authority.
16. Has a history or current evidence of any condition, therapy, or laboratory abnormality that might confound the results of the study, interfere with the subject's participation for the full duration of the study, or is not in the best interest of the subject to participate, in the opinion of the treating investigator.
17. Has known psychiatric or substance abuse disorders that would interfere with cooperation with the requirements of the trial.
18. Patients with allotransplant in past 5 years or those with evidence of graft vs. host disease (GVHD) will be excluded.
19. Have inadequate organ function as defined in the following table (Table 3). Specimens must be collected within 10 days prior to the start of study treatment.

**Table 3** Adequate Organ Function Laboratory Values

System	Laboratory Value
Hematological	
Absolute neutrophil count (ANC)	$\geq 500/\mu\text{L}$ a, b
Platelets	$\geq 50,000/\mu\text{L}$ a, b
Hemoglobin	$\geq 8$ g/dL a, b
Renal	
Creatinine OR Measured or calculated c creatinine clearance (GFR can also be used in place of creatinine or CrCl)	$\leq 1.5 \times \text{ULN}$ OR $\geq 30$ mL/min for participant with creatinine levels $> 1.5 \times$ institutional ULN
Hepatic	
Total bilirubin	$\leq 1.5 \times \text{ULN}$ OR direct bilirubin $\leq \text{ULN}$ for participants with total bilirubin levels $> 1.5 \times \text{ULN}$

AST (SGOT) and ALT (SGPT)	$\leq 2.5 \times \text{ULN}$ ( $\leq 5 \times \text{ULN}$ for participants with liver metastases)
Coagulation	
International normalized ratio (INR) OR prothrombin time (PT)  Activated partial thromboplastin time (aPTT)	$\leq 1.5 \times \text{ULN}$ unless participant is receiving anticoagulant therapy as long as PT or PTT is within therapeutic range of intended use of anticoagulants

ALT (SGPT)=alanine aminotransferase (serum glutamic pyruvic transaminase);  AST (SGOT)=aspartate aminotransferase (serum glutamic oxaloacetic transaminase);  GFR=glomerular filtration rate; ULN=upper limit of normal.
 
aGrowth factor and/or transfusion support is permissible to stabilize participant prior to study treatment if needed.
 
bNo lower limit if cytopenia is related to bone marrow involvement.
 
cCreatinine clearance (CrCl) should be calculated per institutional standard.
 
Note: This table includes eligibility-defining laboratory value requirements for treatment; laboratory value requirements should be adapted according to local regulations and guidelines for the administration of specific chemotherapies.
	

